### **5.4 Preparation and Administration of Study Drug**

Preservative-free ropivacaine 0.25% with 1:300,000 epinephrine will be prepared on day of surgery by diluting ropivacaine 0.5% with sterile saline and adding the appropriate amount of epinephrine. A total of 20ml will be used during adductor canal catheter placement and 20ml will be used in the IPACK block. All drug preparations will be performed by a member of the regional anesthesia team.

### **5.5 Subject Compliance Monitoring**

Study investigators will ensure that correct multimodal therapy is ordered and review the medication record to ensure appropriate administration by nursing.

### **5.6 Prior and Concomitant Therapy**

Patients taking opioid medications daily or almost daily for 3 months or greater preoperatively will not be included in this study.

### **5.7 Packaging**

Not applicable.

### **5.8 Blinding of Study Drug**

Physicians performing the study intervention will not be blinded to the drug or technique. Outcome assessors and patients will be blinded to the study intervention performed.

### **5.9 Receiving, Storage, Dispensing and Return**

#### **5.9.1 Receipt of Drug Supplies**

Upon receipt of the of the study treatment supplies, an inventory must be performed and a drug receipt log filled out and signed by the person accepting the shipment. It is important that the designated study staff counts and verifies that the shipment contains all the items noted in the shipment inventory. Any damaged or unusable study drug in a given shipment (active drug or comparator) will be documented in the study files. The investigator must notify study sponsor of any damaged or unusable study treatments that were supplied to the investigator's site.

#### **5.9.2 Storage**

Study drugs are securely stored in the pyxis and regional anesthesia block cart.

### **5.9.3 Dispensing of Study Drug**

Study drugs will be dispensed from the pyxis and regional anesthesia block cart by a member of the regional anesthesia team on day of surgery.

### **5.9.4 Return or Destruction of Study Drug**

At the completion of the study, there will be a final reconciliation of drug shipped, drug consumed, and drug remaining. This reconciliation will be logged on the drug reconciliation form, signed and dated. Any discrepancies noted will be investigated, resolved, and documented prior to return or destruction of unused study drug. Drug destroyed on site will be documented in the study files.

## **6 Study Procedures**

### **6.1 Day of Surgery (POD #0)**

Prior to regional interventions, patients will be placed on standard ASA monitors with EtCO2 monitoring and supplemental oxygen by nasal cannula. A time out will be performed with the regional team, pre-op nurse, and patient prior to any sedating medications. Sedation will be accomplished with midazolam and fentanyl titrated to patient comfort at the discretion of the regional team.

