# **3 Study Design**

## **3.1 General Design**

Double blinded, randomized controlled trial. All patients who present for primary, unilateral tricompartment TKA will be screened for inclusion. Consecutive patients who meet preset inclusion and exclusion criteria will be recruited either on day of surgery or in the preoperative anesthesia clinic by one of the study investigators. Written consent will be obtained for study participation. Patients who participate will be randomized into one of two treatment arms: continuous ACB with IPACK block versus continuous ACB with sham subcutaneous saline injection. Randomization will be done using the website random.org's Coin Flipper, selecting the Susan B Anthony coin, and flipping 5 coins. Majority heads will be randomized to receive the IPACK block whereas majority tails will be randomized to receive the sham subcutaneous injection. See Attachment A for an example of this website.

CONFIDENTIAL

This material is the property of Ochsner Clinic Foundation. Do not disclose or use except as authorized in writing by the study sponsor

Only the regional anesthesiologist performing the block will know the randomization status. The study participants, outcome assessors/researchers, other anesthesia personnel, surgeons, physician assistants, and nurses will be blinded to the treatment arm. All patients will receive sedation with midazolam and/or fentanyl titrated to comfort during block procedures. Per our standard practice at Ochsner Medical Center, all patients will have either spinal or combined spinal-epidural anesthesia with mepivacaine 1.5% as the primary anesthetic during the surgery and sedation with propofol titrated to comfort. Also per our standard practice at Ochsner Medical Center, multimodal therapy will include ketamine 0.25mg/kg IV (up to 50mg) intraoperatively, dexamethasone 8mg IV intraoperatively, pregabalin 150mg PO preoperatively (adjusted to 75mg for age over 70) followed by 75mg nightly (or home gabapentin dose), acetaminophen 1000mg IV followed by 100mg PO every 6 hours postoperatively, and celecoxib 400mg PO on POD #0 followed by 200mg PO daily.

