### **5.3 Method for Assigning Subjects to Treatment Groups**

Subjects will be randomized to one treatment arm at time of trial enrollment. Randomization will be done using the website random.org's Coin Flipper, selecting the Susan B Anthony coin, and flipping 5 coins. Majority heads will be randomized to receive the IPACK block whereas majority tails will be randomized to receive the sham subcutaneous injection.

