#### *Continuous adductor canal block placement*

A high-frequency linear ultrasound transducer will be used to identify the adductor canal. The transducer will be placed at the mid-thigh, approximately half the distance between the inguinal crease and the patella, and at least 12 cm above the patella. The superficial femoral artery will be identified when it courses dorsal/lateral to the sartorius muscle in the short-axis. The hyperechoic structure located lateral/anterior to the artery will be the target catheter site at the adductor canal. A 17-gauge Tuohy needle will be placed lateral to the superficial femoral artery and within the adductor canal, using an in-plane ultrasound technique by a member of the regional anesthesia team. A total of 20ml of local anesthesia will be injected into the adductor canal. A flexible spring-wound 19-gauge epidural catheter will be advanced 1-2 cm into the adductor canal. The needle will be removed and a test dose of 5ml lidocaine 1.5% with 1:200,000 epinephrine will be injected into the catheter under ultrasound observation. The continuous catheter will be secured with surgical glue and liquid adhesive, and covered with a clear occlusive dressing. The catheter will be attached to a portable electronic infusion pump when the patient reaches PACU. In PACU, an initial 5ml bolus and then 8ml/h continuous infusion of ropivacaine 0.2% will be initiated through the continuous adductor canal catheter.

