#### *IPACK block placement*

A high-frequency curvilinear ultrasound transducer will be used to identify the popliteal artery just proximal to the femoral condyles along the shaft of the femur in the short-axis. A 21g peripheral nerve block needle will be advanced using an in-plane ultrasound technique until the needle tip is located between the popliteal artery and femoral shaft. A total of 15ml of local anesthesia will be injected at this location with an additional 5ml of local anesthesia injected as the needle is withdrawn.

CONFIDENTIAL

This material is the property of Ochsner Clinic Foundation. Do not disclose or use except as authorized in writing by the study sponsor

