### *Sham subcutaneous saline injection*

A high-frequency curvilinear ultrasound transducer will be used to identify the popliteal artery just proximal to the femoral condyles along the shaft of the femur in the short-axis as done with the IPACK block. A total of 1-2 ml of saline will be injected subcutaneously through a peripheral nerve block needle.

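### Nothing delays the performing anesthesiologist's knowledge of the arm until the second injection, so any sedation or shared catheter placement that this physician does may be done unblinded

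*Combined protocol and SAP*

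**What the plan says.** **Allocation.** Section 5.3: "Subjects will be randomized to one treatment arm at time of trial enrollment". Under Section 3.1, patients are "recruited either on day of surgery or in the preoperative anesthesia clinic by one of the study investigators".

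**Who knows.** Section 3.1: "Only the regional anesthesiologist performing the block will know the randomization status". Section 5.8, repeated in 8.4, adds: "Physicians performing the study intervention will not be blinded to the drug or technique". Sections 3.1 and 8.4 list those who stay blinded: participants, outcome assessors and researchers, other anesthesia personnel, surgeons, physician assistants and nurses.

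**Sedation.** Section 6.1: "Sedation will be accomplished with midazolam and fentanyl titrated to patient comfort at the discretion of the regional team". No dose or cap is given. Section 3.1 allows either drug or both, so whether fentanyl is used at all is also a matter of choice.

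**Shared catheter.** Section 6.1 has the adductor canal needle placed "using an in-plane ultrasound technique by a member of the regional anesthesia team". The probe site, needle, target, 20 ml dose, 1-2 cm catheter advance, 5 ml test dose, 5 ml PACU bolus and 8 ml/h infusion are all specified.

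**Second injection.** For IPACK: "A total of 15ml of local anesthesia will be injected at this location with an additional 5ml of local anesthesia" as the needle is withdrawn. For sham: "A total of 1-2 ml of saline will be injected subcutaneously through a peripheral nerve block needle".

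**The concern.** Until the second injection, care is meant to be the same in both arms. An operator who already knows the arm could, without intending to, sedate differently or take more trouble over the catheter in a patient who will receive sham. Section 1.1 describes continuous adductor canal block plus IPACK as common practice at the site, and the study hopes to confirm an earlier favorable review there, so operators may well hold expectations.

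Two things could be touched. The adductor canal block is the analgesic background in both arms, so its quality bears on 24-hour opioid use, the primary endpoint. Preoperative midazolam or fentanyl could also bear on some secondary outcomes, such as over-sedation and nausea or vomiting in PACU. A difference arising in this way would be credited to IPACK although IPACK did not cause it.

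**Working it through.** The plan gives no figure on this point and no arithmetic settles it. The check is to set the relevant sections side by side.

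1. **When does the assignment exist?** At enrollment (5.3), which happens on the day of surgery or in the preoperative anesthesia clinic (3.1). A clinic enrollment fixes the arm at an earlier visit, well before sedation or either block.

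2. **Who may know it?** The regional anesthesiologist performing the block (3.1, 5.8, 8.4). Sections 3.1 and 8.4 require other anesthesia personnel to be blinded.

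3. **When does that physician learn it?** Sections 3.1, 5.3, 5.4, 5.8, 6.1 and 8.4 cover design, assignment, drug preparation, blinding, procedures and unblinding. None of them contains a sealed assignment, a staged disclosure or a separate catheter operator. Section 6.1 describes the catheter before the IPACK and sham injections but does not make that order a rule, and order alone would not delay knowledge of the arm.

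4. **Who does the work before the second injection?** Sedation falls to the regional team and the catheter to one of its members; neither person is further identified. Three cases follow:
   - Another team member does the task. That person must be blinded, so there is no exposure.
   - The performing anesthesiologist does it but has not yet learned the arm. There is no exposure.
   - The performing anesthesiologist does it and already knows the arm. There is exposure.

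   Nothing in the plan rules out the third case.

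5. **How much room is there in those tasks?** Little in the catheter placement, where site, volumes and rates are fixed and mainly the quality of execution can vary. More in sedation, which has no dose limit.

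6. **When is knowledge unavoidable?** At the second injection, because the IPACK and sham techniques differ in depth, drug and volume. No earlier step needs it.

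7. **Can drug preparation reveal the arm early?** Section 5.4 assigns 20 ml of ropivacaine mixture to the catheter and 20 ml to the IPACK block, prepared by a regional team member. An IPACK patient needs 20 + 20 = 40 ml and a sham patient 20 ml. The plan does not say when the second syringe is drawn up. Preparing both at the start would show the arm to whoever prepares them.

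8. **How large could the effect be?** The documents give no fentanyl doses, and nothing on how often the performing anesthesiologist also sedates or places the catheter. No bias figure can be calculated.

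**The case against.** The strongest reply is that the design openly declares an unblinded operator and blinds everyone else who matters. Anyone else who sedates or places the catheter is blinded under Sections 3.1 and 8.4. Sedation is guided by the comfort of a patient who is also blinded. Between block sedation and the postoperative count come spinal or combined spinal-epidural anesthesia, propofol, ketamine and dexamethasone. All of this stands, and it keeps the point small. It does not close the case in which one physician knows the arm and does all the tasks.

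Three stronger readings are tempting, and the documents support none of them.

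- **The whole regional team is unblinded.** A reader might infer this from the wording on sedation. Section 3.1 limits knowledge of the arm to the physician performing the block.
- **Block fentanyl contaminates the primary endpoint.** The Study Summary describes postoperative opioid consumption, and the 24-hour total is placed under the postoperative course in Section 6.2. On that plain reading, preoperative fentanyl adds nothing to the count. Section 3.2 does not say when the 24 hours start, but that is a separate question of endpoint definition.
- **The contrast between the two second injections shows bias.** A deeper injection may call for more fentanyl, but that would follow from the procedure itself at a step where the operator has to know the arm. It says nothing about earlier knowledge, and late disclosure would not remove it.

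**Conclusion.** The point holds in a limited form. The plan leaves open that one physician knows the arm while titrating discretionary sedation or placing the catheter common to both arms, and no procedure requires that knowledge before the second injection. The conclusion rests on two conditions that the plan neither states nor excludes: that the performing anesthesiologist does these tasks, and that this physician has learned the arm by then.

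Any bias is probably small and cannot be sized from the documents. This is a cheap improvement of optional priority. It gives no ground for calling the primary comparison invalid.

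**What to change.** Add to Sections 5.3 and 6.1:

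> *The adductor canal catheter is placed first. The assignment is held in a sequentially numbered sealed envelope, prepared and logged in advance by someone not involved in that patient's care or assessment. The performing anesthesiologist opens it out of the patient's sight only after initial sedation has been given and the catheter has been placed and dosed, immediately before the IPACK or sham injection. The second syringe is drawn up then.*

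The five-coin method can stay, provided the independent person makes and logs the flips when preparing the envelopes.

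As an optional descriptive extra, record block fentanyl with dose and time and report it by arm. Late opening does not equalize fentanyl given during the second injection itself, and the record would make any such difference visible.

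Cost: protocol wording, envelope preparation with a log, and a short pause before the second injection to open the envelope and draw up the syringe. The optional record adds one case report form line. Endpoint, sample size and treatments are unchanged.

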#### *Continuous adductor canal block placement*

A high-frequency linear ultrasound transducer will be used to identify the adductor canal. The transducer will be placed at the mid-thigh, approximately half the distance between the inguinal crease and the patella, and at least 12 cm above the patella. The superficial femoral artery will be identified when it courses dorsal/lateral to the sartorius muscle in the short-axis. The hyperechoic structure located lateral/anterior to the artery will be the target catheter site at the adductor canal. A 17-gauge Tuohy needle will be placed lateral to the superficial femoral artery and within the adductor canal, using an in-plane ultrasound technique by a member of the regional anesthesia team. A total of 20ml of local anesthesia will be injected into the adductor canal. A flexible spring-wound 19-gauge epidural catheter will be advanced 1-2 cm into the adductor canal. The needle will be removed and a test dose of 5ml lidocaine 1.5% with 1:200,000 epinephrine will be injected into the catheter under ultrasound observation. The continuous catheter will be secured with surgical glue and liquid adhesive, and covered with a clear occlusive dressing. The catheter will be attached to a portable electronic infusion pump when the patient reaches PACU. In PACU, an initial 5ml bolus and then 8ml/h continuous infusion of ropivacaine 0.2% will be initiated through the continuous adductor canal catheter.

#### *IPACK block placement*

A high-frequency curvilinear ultrasound transducer will be used to identify the popliteal artery just proximal to the femoral condyles along the shaft of the femur in the short-axis. A 21g peripheral nerve block needle will be advanced using an in-plane ultrasound technique until the needle tip is located between the popliteal artery and femoral shaft. A total of 15ml of local anesthesia will be injected at this location with an additional 5ml of local anesthesia injected as the needle is withdrawn.

CONFIDENTIAL

This material is the property of Ochsner Clinic Foundation. Do not disclose or use except as authorized in writing by the study sponsor

### *Sham subcutaneous saline injection*

A high-frequency curvilinear ultrasound transducer will be used to identify the popliteal artery just proximal to the femoral condyles along the shaft of the femur in the short-axis as done with the IPACK block. A total of 1-2 ml of saline will be injected subcutaneously through a peripheral nerve block needle.

## **6.2 Postoperative Course**

No further procedures are required.

At 24 hours, the cumulative opioid consumption will be summated. An outcomes assessor will survey the patient at pre-specified times for secondary outcomes. Additional secondary outcomes will be pulled from the electronic medical record.

Per standard of care at Ochsner Medical Center, patients that meet clinical milestones will be discharged home on the afternoon of POD#1 with an on-Q pain ball that will be removed by the patient after approximately 48 hours.

## **7 Statistical Plan**

### **7.1 Sample Size Determination**

Prior published literature demonstrates analgesic equivalence between adductor canal block and femoral nerve block. An institutional retrospective study here showed a 38.8% effect difference between femoral nerve block with and without IPACK. Using this information, for an effect size of 0.4, power of 0.8, and significance level of 0.05 we determined a sample size of 64 patients. Assuming a dropout rate of 10%, we will include 72 patients in this study with approximately 36 patients per study arm.

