## Study Summary

Title	Pain after total knee arthroplasty: a comparison of combined continuous adductor canal block with infiltration of local anesthetic between the popliteal artery and capsule of the knee block versus continuous adductor canal block alone on postoperative analgesia
Short Title	IPACK nerve block for total knee arthroplasty
Protocol Number	N/A
Phase	IV
Methodology	Allocation: Randomized Endpoint Classification: Efficacy Study Intervention Model: Single Group Assignment Masking: Double Blind (Outcomes Assessor, patient) Primary Purpose: Treatment
Study Duration	Intervention period immediately prior to surgery with follow-up until hospital discharge
Study Center(s)	Ochsner Medical Center Main Campus
Objectives	To examine the effect of two approaches to nerve blockade on opioid consumption, patient satisfaction, postoperative pain, mobility, length of hospital stay, and several other secondary outcomes.
Number of Subjects	72 total, approximately 36 in each study arm
Diagnosis and Main Inclusion Criteria	
Inclusion Criteria:
 
 
• Unilateral, primary tricompartment total knee arthroplasty
 
• Age 18 years or older
 
• ASA I-III
 
• Eligible for spinal or combined spinal epidural anesthetic
 
• Able to speak, read, and understand English
 
• Willing to participate in the trial
 
• Anticipated discharge home from hospital
 
 
Exclusion Criteria:
 
 
• Contraindication to regional anesthesia or peripheral nerve blocks
 
• Allergy to local anesthetics
 
• Allergy to NSAIDs
 
• Chronic renal insufficiency with Cr > 1.4 or GFR < 60
 
• Have chronic pain that is not related to their knee joint
 
• Have been using opioids on a chronic basis (daily or almost daily opioid use for 3 months or longer)
 
• Have a pre-existing peripheral neuropathy involving the operative site
 
• Body mass index greater than 40
 

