## **1.4 Clinical Data to Date**

No published studies about IPACK exist. An IRB-approved retrospective review of patients at our institution who received IPACK with continuous FNB compared to patients who received FNB alone showed similar VAS pain scores with significantly decreased narcotic requirements postoperatively. The group of patients who received IPACK block had a 38.8% decrease in the mean opioid consumption in the first 24 hours. The same retrospective review showed that patients who received IPACK with continuous ACB had clinically improved performance with physical therapy and a significantly shorter hospital stay.

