### **3.2 Primary Study Endpoints**

- Cumulative opioid consumption (morphine equivalents) in the first 24 hours

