### **7.2 Statistical Methods**

A t-test will be used to compare the two arms of the study. We will apply other statistical methods as per Ochsner's statistics team & researchers.

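### Section 7.1: effect size 0.4, power 0.8 and alpha 0.05 do not yield 64 patients for the planned two-arm t-test, so the stated 80% power is unsupported

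*Combined protocol and SAP*

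**What the plan says.** The sample size rests on one paragraph, section 7.1. Its starting point is the institution's own data: "An institutional retrospective study here showed a 38.8% effect difference between femoral nerve block with and without IPACK". The calculation follows: "for an effect size of 0.4, power of 0.8, and significance level of 0.05 we determined a sample size of 64 patients". The last step is: "Assuming a dropout rate of 10%, we will include 72 patients in this study with approximately 36 patients per study arm". The Study Summary repeats the result: "72 total, approximately 36 in each study arm".

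Three other places fix the setting:

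- Section 1.4 gives the scale of the 38.8%: the IPACK group "had a 38.8% decrease in the mean opioid consumption in the first 24 hours". It is a relative change in a mean.
- Section 3.2 names a single, continuous primary endpoint: "Cumulative opioid consumption (morphine equivalents) in the first 24 hours".
- Section 7.2 names the test: "A t-test will be used to compare the two arms of the study".

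The documents do not say what kind of effect size 0.4 is, whether the test is one- or two-sided, what mean and SD of opioid consumption were assumed, or which formula or software was used.

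**The concern.** A t-test calculation needs a difference and an SD, or their ratio. Section 7.1 gives one unlabelled number. The wording "Using this information, for an effect size of 0.4" ties that number to the 38.8%, a percentage change that carries no information on variability. If 0.4 is instead taken as a standardised effect, the usual calculations give totals well away from 64.

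This paragraph is the only justification of the sample size, and it serves the only primary endpoint. As it stands, a reader cannot tell what difference in 24-hour morphine equivalents the trial can detect, or with what power. A null result would then be hard to interpret, because 32 per arm could have well above or well below 80% power for the effect the sponsor has in mind.

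**Working it through.** **Inputs**

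| Input | Value | Source |
|---|---|---|
| Effect size | 0.4, metric not stated | 7.1 |
| Basis for it | 38.8% decrease in mean 24-hour opioid use | 7.1, 1.4 |
| Power, alpha | 0.80, 0.05 (sidedness not stated; both tried) | 7.1 |
| Test | two-arm t-test | 7.2 |
| Mean, SD or CV | not given | – |
| Dropout, final size | 10%, 72, about 36 per arm | 7.1 |

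**Step 1: the plan's own figures.** 64/0.9 = 71.1, rounded up to 72, or 36 per arm. The dropout step reproduces. It also shows that 64 is a total, 32 evaluable per arm. What remains is whether the inputs give 64.

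**Step 2: method.** For a standardised difference d, the normal approximation is n per arm = 2(z₁₋α/₂ + z₁₋β)²/d². The figures below use exact noncentral-t power. They are two-sided unless stated, with n rounded up in each arm.

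**Step 3: 0.4 as the 38.8% relative decrease.** Here d = 0.388/CV if both arms share one SD, where CV is the control-arm SD divided by its mean. If both arms have the same CV, d = 0.388/(CV × √((1 + 0.612²)/2)) = 0.388/(0.829 × CV). Without a CV there is no N. The CV range below is an assumption, because the documents give none.

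| Assumed CV | Power at 32 per arm, common SD | Total for 80%, common SD | Power at 32 per arm, same CV | Total for 80%, same CV |
|---|---|---|---|---|
| 0.4 | 0.969 | 36 | 0.996 | 26 |
| 0.5 | 0.863 | 56 | 0.958 | 38 |
| 0.6 | 0.721 | 78 | 0.867 | 54 |
| 0.8 | 0.480 | 136 | 0.635 | 94 |
| 1.0 | 0.333 | 212 | 0.454 | 146 |

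With 32 per arm, 80% power needs d = 0.711. Solving for CV gives 0.388/0.711 = 0.545 (common SD) or 0.545/0.829 = 0.66 (same CV). One-sided, the required d is 0.629 and the CVs are 0.62 and 0.74.

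**Step 4: 0.4 as a standardised difference.** Normal approximation: 2(1.960 + 0.842)²/0.16 = 98.1, so 99 per arm. Exact t: 99.1, so 100 per arm and 200 in total. One-sided: 78 per arm, 156 in total. Power at 32 per arm is 35% two-sided and 48% one-sided.

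**Step 5: 0.4 as Cohen's f.** For two equal groups d = 2f = 0.8. Exact t: 25.5, so 26 per arm and 52 in total (42 one-sided). Power at 64 is 88%, not 80%.

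**Step 6: other readings.** None of these returns 64: paired or one-sample d = 0.4 (52), correlation of 0.4 (47), chi-square w = 0.4 on 1 df (50), or two proportions differing by 0.4 (40 to 48 in the cases tried, 50 to 58 with continuity correction). Two coincidences should be noted. A three-group one-way ANOVA with f = 0.4 needs 63.3 in total, but this trial has two arms. A two-sided t-test with d = 0.5 needs 63.8, so 64, per arm, but section 7.1 states 0.4 and uses 64 as a total. The documents do not say that either was the source.

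**Step 7: simulation check.** With 40,000 normal trials per case at 32 per arm and a pooled t-test, power was 0.353 at d = 0.4, 0.880 at d = 0.8, 0.802 at CV 0.545 (common SD) and 0.798 at CV 0.658 (same CV).

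**The case against.** The strongest reply is that 0.4 is plainly the 38.8% rounded, and that on this reading 64 is undetermined rather than contradicted. The sponsor may have taken an SD from the retrospective review and not printed it, and a CV of 0.545 or 0.66 lies inside the range tried above. On that view this is an unreported input, not an arithmetic error. The reading is fair, and it is why nothing here says that the trial is underpowered. It does not rescue the stated 80%, because the inputs as printed still lead to no number. If an SD was used, it needs to be printed.

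The CV range of 0.4 to 1.0 is assumed, and nothing in the documents supports either end. That stands. The spread in power shows only how much depends on the missing SD.

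Section 4.4.2 keeps withdrawn patients in the intention-to-treat analysis, so up to 72 might be analysed. At 36 per arm the detectable standardised difference is 0.67 instead of 0.71, the CVs for 80% power are 0.58 and 0.70, and power is 39% at d = 0.4 and 92% at d = 0.8. The shift is modest, and section 7.1 itself bases the power on 64.

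Finally, the remedy leaves the size, endpoint and test unchanged, and restating a target with N already fixed invites choosing inputs to match 64. The risk is real. It is a reason to take the SD from the review's data and not solve for it backwards.

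**Conclusion.** The concern holds. For a two-arm t-test, the stated effect size, power and significance level do not lead to 64 patients. Taken as a standardised difference, 0.4 requires about three times that number (200/64 = 3.1). Taken as Cohen's f, it requires 12 fewer. Taken as the relative decrease the paragraph points to, it gives no number at all.

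The direction of any error is unknown. Over the assumed CV range, the risk of missing a true 38.8% decrease with 32 per arm runs from 3% to 67% (common SD) or from under 1% to 55% (same CV). One figure does not depend on how 0.4 is read: with 32 evaluable patients per arm and a two-sided 0.05 test, 80% power is reached at a standardised difference of 0.71. All figures assume equal arms and the t-test's normal model.

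**What to change.** Rewrite section 7.1 and keep the planned 72.

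1. Replace the unlabelled 0.4 with the target difference in 24-hour morphine equivalents, the assumed mean in each arm, the SD and the sidedness. Take the SD from the institution's retrospective review. If the review holds none, give a stated range of CV.
2. Restate the power that 64 evaluable patients (32 per arm) give for that target.
3. Add a sentence such as: 32 evaluable patients per arm give 80% power for a standardised difference of about 0.71 (two-sided 0.05). The figure for 36 per arm, 0.67, can stand beside it.
4. Give 35% power only if the sponsor confirms that 0.4 was a standardised difference. If it was Cohen's f, say so and give 88%.

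Optionally, section 7.2 could say that the primary result will be reported as a difference in means with its 95% confidence interval. The expected half-width is t(0.975, 62 df) × √(2/32) = 2.00 × 0.25 = 0.50 SD.

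The cost is one paragraph and one calculation. The downside is that the restated power may be less favourable than 80%, or may have to be given as a range.
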